This can include prevention, diagnostic or therapeutic interventions (e.g., drug or device) or educational, health services or basic science interventions (e.g., educational program, health care delivery model, or examining basic physiology)

Behavioral lifestyle intervention: Participants (N=40) will be randomized to the mHealth+ group Intervention group (Group A; n=20) and mHealth+ individual intervention group (Group B; n=20) group using a block randomization table. (1) The mHealth+ group Intervention group (Group A) will receive a modified Look AHEAD behavior lifestyle intervention with smartphone-based self-monitoring of diet and physical activity. This comprises ten group sessions for lifestyle intervention in 6-months. The group will receive three weekly classes in the first month and then bi-weekly classes for month 2-3, and three monthly session in month four, five, and six. The frequency and layout of these classes will allow participants to master new skills gradually, then eventually wean off, and adopt the modified lifestyle as the part of their daily lives. (2) The mHealth+ individual intervention group (Group B) will receive an abbreviated behavior lifestyle intervention with smartphone-based self-monitoring of diet and physical activity in one face-to-face individual session at the beginning of the study. In addition, participants will receive self-study materials, from Look Ahead modules, and a monthly follow-up phone calls for the duration of the study (6-months). The goal for these follow up phone calls are to assess understanding of the modules, to promote continued engagement with the study material, and to provide clarification on materials as needed. Participants in the mHealth+ group Intervention group (Group A) and mHealth+ individual intervention group (Group B will receive instruction on how to download an app to help them record their diet and physical activity at the beginning of the study. (see updates to study protocol dated below)

Fitbit offers a simple, easy-to-use tool for tracking food and physical activity. It helps set daily calorie budget, and set and work towards goals for nutrient intake, weight loss, exercise, and more. https://www.fitbit.com/inspire

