10.1. Measures to Minimize Bias: Randomization and Blinding

This section should contain a description of randomization and blinding procedures (if applicable to the study design). It should include a description or a table that describes how study participants will be assigned to study groups, without being so specific that blinding or randomization might be compromised. Plans for the maintenance of trial randomization codes and appropriate blinding for the study should be discussed. The timing and procedures for planned and unplanned breaking of randomization codes should be included. Include a statement regarding when unblinding may occur and who may unblind. Provide the criteria for breaking the study blind or participant code. Discuss the circumstances in which the blind would be broken for an individual or for all participants (e.g., for serious adverse evets (SAEs)). Indicate to whom the intentional and unintentional breaking of the blind should be reported.

The PI will not be blinded by the study mHealth+ group Intervention group and mHealth+ individual intervention group.

Participants (N=40) be randomized into two groups using a block randomization table to receive behavioral lifestyle educational intervention. Everyone will receive a baseline and end of study visits.

We divided our future participants into 4 groups (10 - (group A):10- (group A):10- (individual B):10 (individual B) and with the help of computer generated program, we will start our intervention group (Group A - n=20) first followed by our control group (Group B - n=20). (see updates dated below)

Participant in mHealth + group intervention (Group A) you will receive a total of 10 group sessions in 6-months. The group will receive 3 weekly classes in the first month and then bi-weekly classes for month 2-3, and three monthly session in month four, five, and six.

10.20.2020: we completed up to three face to face group intervention sessions (Group A) over WebEx due to COVID-19 restrictions.

10.20.20: we finished our participants (N=20) in the group intervention and due to COVID-19 restrictions we were not able to enroll our participants for the control group.

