After discussing with IRB person and mentors, we decided to not to enroll participants for the Group B due to highrisk for COVID-19. We were able to receive enough information from the Group A intervention participants and to finish enrolling participants for the pilot study. Modification due to Pandemic, forgoing control arm, and worked with the interventional participants still worked with the study data to meet study aim-the deviation related to COVID-19 did not impact subject rights, safety, welfare, or the overall integrity of the science of the study.

7

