12.4. Statistical Analyses

Include analysis of primary efficacy endpoints, secondary endpoints, safety analyses, and any planned interim analyses

The impact of the intervention on frailty status (non-frail, pre-frail, frail) and frailty score (0, 1, 2, 3, 4, or 5) over the 6month period (from baseline to follow-up) will be assessed by proportional odds cumulative logit (POCL) model to assess the log-odds of frailty as an indicator of being exposed to the intervention. The initial POCL model will adjust only for the baseline value of frailty status. A subsequent model will adjust for baseline age, sex, ethnic group, BMI, and Hba1c, to determine potential covariate interactions with the intervention. Continuous secondary outcomes including fasting glucose, Hba1c, and BMI will be assessed using linear regression with intervention, baseline frailty, sex, and ethnic group as categorical predictor variables and baseline age, BMI, and Hba1c as continuous predictor variables. The categorical outcomes SPPB and PROMIS scores will also be evaluated using the POCL model. Because the POCL model is complex and this is a pilot study, it is not practical or feasible to do a power analysis for the given experimental design but based on the work of Drs. [name] and [name], we believe at least 20 participants in the group (mHealth+ group Intervention group) are needed. The effect of the intervention on the change in frailty category and/or frailty scores will be used to calculate power and sample size estimation for a future, larger study.

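### With the control arm dropped, the models in 12.3/12.4 put about 8 to 14 parameters on at most 20 people, with no rule for sparse data

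*Combined protocol and SAP*

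**What the plan says.** Sections 12.3 and 12.4 carry the same analysis text. Frailty status (three levels) and frailty score (0 to 5) are to be analysed by a proportional odds cumulative logit (POCL) model. The first version is small: "The initial POCL model will adjust only for the baseline value of frailty status". It is then enlarged: "A subsequent model will adjust for baseline age, sex, ethnic group, BMI, and Hba1c", with the aim of finding interactions between covariates and intervention. Fasting glucose, HbA1c and BMI are each analysed by "linear regression with intervention, baseline frailty, sex, and ethnic group as categorical predictor variables and baseline age, BMI, and Hba1c as continuous predictor variables".

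This model list belongs to the design in Section 7: "Participants (N=40) will be randomized to the mHealth+ group Intervention group (Group A; n=20"), with another 20 in Group B. The October 2020 updates in Sections 7 and 10.1 report that "we finished our participants (N=20) in the group intervention", and Section 10.1 adds that "we decided to not to enroll participants for the Group B due to highrisk for COVID-19". Sections 12.3 and 12.4 were not revised to match. They contain no rule for sparse categories, separation, penalisation or dropping covariates.

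**The concern.** A model list written for 40 people in two arms is now to be fitted to one arm of at most 20. Two things can go wrong.

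- **Frailty, the primary outcome.** An ordinal model with few people and several categorical terms can be separated: some combination of predictors orders the outcome perfectly, and at least one coefficient is infinite. Software then reports non-convergence or very large standard errors.
- **Secondary outcomes.** A linear model with many terms for few people shows a sizeable R-squared by chance and predicts poorly.

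Sections 12.2 and 12.4 say the frailty results will feed the sample size of a larger study, so unstable estimates would be carried forward. With one arm, the covariates correct no imbalance between groups; they cost degrees of freedom without protecting against bias.

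**Working it through.** **The plan's own figure.** Section 12.4 says "we believe at least 20 participants in the group (mHealth+ group Intervention group) are needed" and that "it is not practical or feasible to do a power analysis for the given experimental design". No power, alpha, effect size or variance is given, so the 20 cannot be reproduced.

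**Inputs from the documents.** n is at most 20 (Sections 7 and 10.1). Section 10.2 names attrition as a risk but gives no rate. Status has 3 levels (2 thresholds) and the score 6 levels (5 thresholds). Covariates are as listed in 12.4.

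**Assumed.** Ethnic group has 2 to 4 levels (1 to 3 df). Baseline status is a category (2 df) and is retained in the adjusted POCL model. The intervention term and its interactions are removed because they are constant or undefined in one arm.

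**Parameter count.** Slopes: frailty 2 + sex 1 + ethnic group 1 to 3 + age, BMI and HbA1c 3 = 7 to 9.

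| Model | Count | Total |
|---|---|---|
| Linear | 1 intercept + 7 to 9 | 8 to 10 |
| Adjusted POCL, status | 2 thresholds + 7 to 9 | 9 to 11 |
| Adjusted POCL, score | 5 thresholds + 7 to 9 | 12 to 14 |

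If the adjusted POCL model does not retain baseline status, which 12.4 leaves open, the totals are 2 + 5 to 7 = 7 to 9 (status) and 5 + 5 to 7 = 10 to 12 (score).

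**Information in a three-level outcome.** Effective n = n − Σnⱼ³/n². For counts 7/10/3: 20 − 1370/400 = 16.6. For 6/12/2: 20 − 1952/400 = 15.1. For 5/10/5: 20 − 1250/400 = 16.9.

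**Existence of a finite POCL estimate, n = 20.** Datasets were simulated and each was tested for complete or quasi-complete separation by linear programming. Assumptions: baseline non-frail/pre-frail/frail mixes of 35/50/15, 30/60/10 and 25/50/25; 60-75% stay in category and the rest move one step; three ethnic groups; covariates unrelated to outcome.

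| Status model | Baseline as 2-df category | Baseline as one ordered term |
|---|---|---|
| Baseline only | no finite estimate in 40-76% | 4-25% |
| Adjusted | 57-84% | 30-54% |

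The low ends of the adjusted rows shift noticeably with the assumed sex and ethnic mix, so all of these are approximate.

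**Wider assumptions.** Four frailty mixes (40/50/10, 30/50/20, 33/33/33, 20/70/10), latent correlation of 0, 0.5, 0.7 or 0.85 between baseline and follow-up, and 2 to 4 ethnic groups give 4 × 4 × 3 = 48 settings. The adjusted status model has no finite estimate in 6-94% of datasets, and in more than half of them in 31 of the 48 settings. The categorical baseline-only model fails in 3-79%. The adjusted score model fails in 6-76%, exceeding 50% in 3 of 8 settings.

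**Linear models.** Residual df = 20 − 8 = 12 down to 20 − 10 = 10. If no predictor is related to the outcome, expected R-squared = p/(n − 1): 7/19 = 0.37 to 9/19 = 0.47. If one predictor is the outcome's own baseline, the result depends on how strongly it tracks:

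- Correlation 0.9 (true R-squared 0.81): apparent 0.87-0.89, out-of-sample 0.65-0.71.
- Correlation 0.5 (true 0.25): apparent 0.51-0.59, out-of-sample −0.15 to −0.40.

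**After reduction to the outcome's own baseline.** Residual df = 20 − 2 = 18 and R-squared expected from noise = 1/19 = 0.05. At correlation 0.7 (true 0.49), out-of-sample R-squared is 0.45, against 0.22 (two ethnic groups) or 0.06 (four) for the full model.

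**The case against.** The strongest reply is that the covariates are not the main cause of separation. Most of it is already present in the baseline-only model, which has four parameters, and it falls sharply when baseline status is one ordered term. For the POCL model, 12.4 does not say how baseline status is coded; it specifies categorical coding only for the linear models. This stands. The covariates add to the risk, but the 2-df coding drives much of it.

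A reader might infer that the frailty model will usually have no finite solution. The documents do not support that. They give no frailty mix, no stability of frailty over six months and no number of ethnic groups. Across plausible values the risk runs from small to near certain, and for the score model it is below one half in most settings tried.

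A reader might also infer that the secondary regressions will largely fit noise. That fails for HbA1c and BMI, whose models contain their own baseline values; where these track follow-up closely, most of the fitted variation is real. Nor should one quote 1 − 0.95⁸ = 34% as the chance of a spurious covariate finding. That treats eight tests as independent, simulation gives about 25%, and the plan promises no covariate tests beyond the interactions.

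It is also fair to say that this is a pilot, that the adjusted model is secondary to the initial one, and that losing the control arm is the larger defect. Pilot status does not excuse it, since the estimates are meant for planning. Correcting only the intervention term would leave the covariate load in place.

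**Conclusion.** The point holds in this form: for at most 20 people, 12.3/12.4 prescribe linear models with 8 to 10 coefficients and adjusted POCL models with 9 to 14 parameters, without a safeguard. The counts rest on 2 to 4 ethnic groups and categorical baseline status retained in the adjusted model.

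The frailty-status model carries a substantial risk of having no finite estimate, but its size depends on inputs the documents do not give, and the simulated ranges should be read as conditional on them. The linear models are weakest for fasting glucose, whose own baseline is not a listed predictor; the problem is smaller for HbA1c and BMI. The plan should be changed, at little cost. The change does not restore an intervention effect, which one arm cannot estimate from these models.

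**What to change.** In Sections 12.3 and 12.4:

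1. Delete the second, covariate-adjusted POCL model.
2. Reduce each secondary linear model to the outcome's own baseline, with change from baseline as the quantity estimated. For fasting glucose, add its baseline value as the predictor. Section 8.4 schedules a chemistry panel at baseline and end of study, but the text should confirm that the glucose sample is a fasting one.
3. If an ordinal regression for frailty is kept, enter baseline frailty as a single ordered term and fit by penalised likelihood (Firth-type or similar). The ordered term alone does not remove the risk of separation.
4. Report age, sex, ethnic group, BMI and HbA1c descriptively.

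The cost is a few lines of text and no additional assessments. The downside is that covariate associations are no longer modelled, which 20 people could not support reliably. The intervention term and its interactions, which cannot be estimated with one arm, need a separate correction.

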3. Objectives and Endpoints All data points collected in the study should support an objective or have a regulatory *purpose.*

Complete the table – add rows as needed.

3.1. Objective(s) Clearly and concisely define the primary and secondary outcomes.	3.2. Endpoint Clearly define the endpoints. (endpoints are the basis for concluding that the objective has been met).	3.3. Justification for Endpoint Briefly explain why the endpoint(s) were chosen.
Determine the feasibility of the	Results from this study will	Behavioral lifestyle interventions using a
lifestyle intervention using a	provide the first information	smartphone for self-monitoring to
smartphone for self-monitoring of	regarding the efficacy of a	improve frailty measurements, body
diet and physical activity for the	behavioral lifestyle intervention	weight, and glycemic control in
improvement of frailty measurements	using a smartphone in the	overweight/obese older adults with T2D.

19-019H, [name], Form CT, 10-20-20, AMD

2

(primary outcome) and on weight management and glycemic control (secondary outcomes) in	improvement of frailty measurements in community- dwelling older adults with T2D.	
overweight/obese older adults with T2D.		

4. Rationale

Briefly state the reason for conducting the clinical trial.

Despite the significant prevalence of T2D among older adults and/or those with multiple comorbidities, these populations have been excluded from randomized controlled trials of treatments for T2D and its associated conditions. Based on the prevalence of T2D, its related complications, implementation of cost-effective treatment and up to date (or less burdensome) self-monitoring strategies for overweight/obese older adults with T2D, this study is needed.

5. Study Design: Randomized controlled trial																		
5.1. Number of					Group name(s)			mHealth+ group Intervention group										
Gro	oups/Arms								sup name(s) initiation group intervention group									
5.2.	Overall Des	sign																
Sele	ct all applic	able																
	□ Randomization								(Cluster I	Rando	omize	d					
	□ Group-Sequential						A	Adaptive	e Desi	gn								
	Parallel Design						P	Placebo-Controlled										
□ Superiority						F	Equivalence 🛛 Non-inferiority					y						
	Device		Pil	lot					P	Pivotal 🗆 Post-Approval								
Drug/Biologic \Box $Phase_1$ \Box Phase 1/2			e 1/2	: [Phase	2		Phase 2/3		P	hase 3		Phase 4				

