8.4. Laboratory Tests

Laboratory tests: Complete blood count, chemistry with liver function tests, lipid profile, HbA1c, and inflammatory markers (CRP, IL6) will be collected from all participants. Approximately 28 ml of blood will be collected at baseline and at end of study for clinical labs and quantifying proteins of interest. Approximately 16 ml of blood will be collected in a serum separating tube and will be used for clinical lab values (complete metabolic panel, lipids and A1c). The remaining 12 ml of blood will be collected in an EDTA tube and will be used to quantifying circulating cytokines.

04.12.20: Due to COVID-19 and social distancing order, we will be adding hemoglobin Hba1c home test for our eight participants who are finishing the study on April 20, 2020. We will continue to our virtual behavioral education session and will collect other end of study assessments virtually.

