8.6. Other Research Procedures (e.g., other safety and efficacy assessments.)

Frailty assessment: We will conduct the assessment at the baseline and then at the end of the study. Frailty is defined as the presence of $\geq 3/5$ of characteristics 1) self-reported unintentional weight loss of ≥ 10 pounds in last year, 2) self-reported exhaustion, 3) low physical activity based on the Minnesota Leisure Time Physical Activity Questionnaire, 4) weak handgrip, 5) and slowness on a 10-foot walk at the usual pace. These measures have been standardized in SALSA study ^{7,21} and will be used in this study. Pre-frailty is defined as 1 or 2 of these characteristics and Non-frailty is defined as the presence of 0 characteristics. As a measure of lower extremity function, we will use the Short Physical Performance Battery (SPPB).²² All participants regardless of frailty status are eligible for study inclusion.

5

History and Physical Assessment: We will document participants' medical history regarding his/her diagnosis of T2D, length time having T2D, and use of any glucose-lowering medications and/or insulin. Height, weight, waist circumference, and vital signs (blood pressure, heart rate, temperature, and respiration) will be measured. Patient-Reported Outcomes Measurement Information System (PROMIS): PROMIS-Global Health (GH) and PROMIS-57 questionnaires, and a single-item Binge eating question will be completed by all participants at the baseline and end of study visit. In addition, all participant will complete focus group questionnaires at the end of study visit. For this study, we will recruit 20 participants for group intervention. All participants will receive a baseline and end of study visit. Participants in the group intervention will receive 10 behavioral education sessions. We will have 4-8 participants in each group intervention The focus group will be conducted at the end of study visit and procedures (session 10, visit 11) for the group intervention population. Participants will be informed in the consent and once

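### With only Group A enrolled, the linear model for fasting glucose, HbA1c and BMI has no estimable intervention effect and no stated within-person change, and the glucose model also lacks its own baseline

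*Combined protocol and SAP*

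**What the plan says.** Sections 12.3 and 12.4 carry the same analysis text. For the continuous secondary outcomes it says: "Continuous secondary outcomes including fasting glucose, Hba1c, and BMI will be assessed using linear regression". The categorical terms of that model are the intervention itself, frailty at entry, sex and ethnicity. The continuous terms are given as "baseline age, BMI, and Hba1c as continuous predictor variables". The text does not say whether the response is the end-of-study value or the change from baseline.

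Section 8.4 schedules the blood: "Approximately 28 ml of blood will be collected at baseline and at end of study for clinical labs and quantifying proteins of interest". The serum tube "will be used for clinical lab values (complete metabolic panel, lipids and A1c". Glucose is not named there, and the section does not say whether the draws are fasting.

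The objectives table in section 3 names "weight management and glycemic control (secondary outcomes") without listing fasting glucose, which appears only in 12.3 and 12.4.

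The October 2020 updates in sections 7 and 10.1 report that the 20 Group A participants finished and that Group B was not enrolled. The regression text was not changed to match.

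**The concern.** Two things are wrong with the linear model as it stands.

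First, it was written for two arms and only one exists. Its target, the intervention coefficient, has no comparison group, and the text names nothing to replace it. In a single arm the natural quantity is mean change from baseline over six months, and the plan does not ask for it.

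Second, one covariate list serves three outcomes. HbA1c and BMI happen to be on the list, so those two outcomes are adjusted for their own baselines. Fasting glucose is not, even though a baseline value should be available.

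At stake is whether the weight and glycaemic-control results have a defined estimand. For glucose, there is also variation that its own baseline might remove.

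**Working it through.** The plan gives no correlation, standard deviation, effect size or alpha for these outcomes. Its figure of at least 20 in Group A (12.2) has no inputs attached, so there is nothing to reproduce. The check covers estimability first, then precision under stated assumptions.

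**1. Estimability.** Assume three frailty levels (as defined in 8.6) and two ethnic groups. The columns are intercept 1, intervention 1, frailty 2, sex 1, ethnic group 1, and age, BMI and HbA1c 3, so 9 in total.

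- Two arms of 20: rank 9, residual df = 40 - 9 = 31.
- Group A only, n = 20: the intervention column equals the intercept column, so rank is 8 of 9 and residual df = 20 - 8 = 12.

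The intervention coefficient is therefore not estimable. Adding baseline glucose does not change that, and the result is the same for all three outcomes.

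**2. Why the unstated response matters most for glucose.** If an outcome's own baseline is a covariate, regressing the end value or the change gives the same fit and the same coefficients on every other term; only the own-baseline coefficient shifts, by 1. For HbA1c and BMI the ambiguity is therefore harmless to the other coefficients. For glucose, with no own baseline, the two are different models.

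**3. Precision from adding baseline glucose.** All three correlations are assumptions:

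- r1, baseline with end glucose: 0.5-0.7
- r2, baseline HbA1c with end glucose: 0.4-0.6
- r12, baseline HbA1c with baseline glucose: 0.7-0.8

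With HbA1c alone, R² = r2². With both, R² = (r1² + r2² - 2·r1·r2·r12)/(1 - r12²). The proportional fall in residual variance is (r1 - r2·r12)² / [(1 - r12²)(1 - r2²)], and the SE ratio is the square root of one minus that.

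| r1 | r2 | r12 | Fall in variance | Fall in SE |
|---|---|---|---|---|
| 0.5 | 0.6 | 0.8 | 0.0004/0.2304 = 0.2% | 0.1% |
| 0.5 | 0.4 | 0.7 | 0.0484/0.4284 = 11.3% | 5.8% |
| 0.7 | 0.6 | 0.8 | 0.0484/0.2304 = 21.0% | 11.1% |
| 0.7 | 0.4 | 0.8 | 0.1444/0.3024 = 47.8% | 27.7% |

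The first and last rows are the extremes of the assumed ranges: about 0-48% in variance and 0-28% in SE, before the loss of one df (12 to 11 once the intervention term is gone).

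**4. Adding versus substituting.** Replacing HbA1c by baseline glucose changes residual variance by (1 - r1²)/(1 - r2²). At r1 = 0.5 and r2 = 0.6 this is 0.75/0.64 = 1.17, a 17% rise in variance and, since √1.17 = 1.08, an 8% rise in SE. Substitution can do harm; addition cannot, apart from the df.

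**5. What a paired change would deliver.** With n = 20 complete pairs and equal SDs at the two visits, the 95% half-width is 2.093 × √(2(1 - r)/20) SD: 0.55 at r = 0.3, 0.47 at 0.5, 0.36 at 0.7 and 0.30 at 0.8. This depends on the baseline-to-end correlation, not on the covariate gain in step 3.

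**The case against.** A reader might infer that the covariate omission leaves glucose without any within-person change. The documents do not support that. Chemistry is scheduled at both visits, so pairs can exist if the panel includes glucose, and the response could even be intended as change. Nor does a baseline covariate by itself define a mean change: HbA1c and BMI have theirs, and the model as written specifies no mean change for them either. The missing comparison comes from the dropped arm and affects all three outcomes.

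A reader might also infer that non-fasting glucose will be analysed as fasting. That goes too far. No section describes a non-fasting draw, and the Schedule of Activities is attached as a separate file that is not shown. The link to the last group session ("The focus group will be conducted at the end of study visit and procedures (session 10, visit 11")) says nothing about meals. For eight participants that session was virtual and the face-to-face blood test was deferred until distancing ended (section 7), so their draw need not coincide with it. What remains is that the fasting state cannot be confirmed from the text available.

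The precision argument can also be called weak, because baseline HbA1c may already be an adequate proxy. That stands: the gain is close to zero at one end of the assumed ranges. Finally, HbA1c also covers glycaemic control, so the consequence for the trial is limited.

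None of this answers the core point. The model's intervention effect is inestimable, no change is specified in its place, and a baseline that should be on file is left out of one model.

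**Conclusion.** The point holds, at modest priority. As written, the linear regression gives no estimable intervention effect for fasting glucose, HbA1c or BMI and specifies no within-person change. That part follows from the enrolment of Group A alone; the coding assumptions in step 1 affect only the degrees of freedom.

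The glucose model also omits its own baseline. This rests on the assumption that glucose is part of the metabolic panel. The size of that omission is not determined by the documents: about 0-48% of residual variance and 0-28% of the standard error under the stated correlation ranges. It should not be reported as a known loss. The fasting question is a check to make, not a demonstrated error.

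**What to change.** In 12.3 and 12.4:

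- Analyse fasting glucose, HbA1c and BMI in the single arm as paired within-person change from baseline to end of study, each with a 95% CI.
- In any regression that is kept, drop the intervention term, state the response, and add baseline glucose to the covariates of the glucose model. Add it to baseline HbA1c; do not substitute it.
- As a secondary check, confirm fasting status at both draws from the Schedule of Activities and visit records. If it was not recorded, label the result 'glucose, fasting status unknown'. Do not remove the outcome: Group A has finished, so removal now would be a post hoc change of outcomes.

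The cost is one residual degree of freedom in the glucose model, a look at the visit records and a little more analysis work. No new data are needed if glucose was reported with the panel.

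### SPPB and PROMIS are sent to a proportional odds model that omits their own baselines and, with only one arm enrolled, has no estimable intervention term

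*Combined protocol and SAP*

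**What the plan says.** Sections 12.3 and 12.4 carry the same analysis text. For these two measures it reads: "The categorical outcomes SPPB and PROMIS scores will also be evaluated using the POCL model". That sentence names no covariates and no score levels.

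The POCL model is described just before it, for frailty, with two covariate sets:

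- First: "The initial POCL model will adjust only for the baseline value of frailty status".
- Then: "A subsequent model will adjust for baseline age, sex, ethnic group, BMI, and Hba1c, to determine potential covariate interactions with the intervention".

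The linear regressions for the continuous secondary outcomes include "baseline age, BMI, and Hba1c as continuous predictor variables", so BMI and HbA1c are adjusted for their own baselines there.

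Section 8.6 shows that the baselines exist. The PROMIS questionnaires "will be completed by all participants at the baseline and end of study visit". SPPB is described within the frailty assessment, of which the section says "We will conduct the assessment at the baseline and then at the end of the study".

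On design, section 7 first states: "Participants (N=40) will be randomized to the mHealth+ group Intervention group (Group A; n=20"), with 20 more in Group B. The updates of 20 October 2020 in sections 7 and 10.1 then record that the 20 group-intervention participants finished and that enrolment to Group B was abandoned. Section 12 was not revised to match.

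**The concern.** Two gaps meet in one sentence. First, as written, the SPPB and PROMIS models adjust for frailty status at baseline, and later for demographic and metabolic variables, but not for where each person started on the score being analysed. The plan does make that adjustment for frailty, BMI and HbA1c.

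Second, the sentence presupposes a contrast between groups. With one group enrolled, the model has nothing to contrast, and the baseline value that it leaves out is the only reference left. Followed literally, the plan gives no usable estimate for either measure, although the paired data were planned for collection.

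The missing score levels add to this. Frailty has its levels spelled out (three categories, or a score of 0 to 5). SPPB and PROMIS are called categorical with no levels, so the analyst would have to choose any grouping later.

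**Working it through.** **Plan's own figure.** There is none to reproduce. Section 12.2 gives at least 20 participants in the group arm, without alpha, power, effect size or SD, and says that no power analysis was done.

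**1. Is own baseline in either covariate set?**

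| Outcome | Model in 12.4 | Own baseline listed? |
|---|---|---|
| Frailty status | POCL | Yes |
| BMI, HbA1c | Linear | Yes |
| Fasting glucose | Linear | No |
| SPPB, PROMIS | POCL | No |

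**2. Can the intervention term be estimated with one arm?** Write the model as logit P(Y ≤ j) = α_j − βT − γF, where T is intervention and F is baseline frailty. If T = 1 for all 20 people, only α_j − β enters the likelihood: adding any constant to β and to every α_j changes nothing. A numerical check agrees. A design matrix with columns for intercept, intervention and frailty has rank 2 of 3. Adding own baseline as a further column leaves T identical to the intercept, so covariates alone do not solve the problem.

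**3. What can one arm estimate?** Mean within-person change. In units of the score's SD, with equal SDs at both visits and correlation r between them, SE = √(2(1 − r)/20). The documents give no r, so a range is assumed. The half-width uses t = 2.093 on 19 degrees of freedom, and 20 complete pairs are assumed.

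| r | SE of mean change (SD) | 95% CI half-width (SD) |
|---|---|---|
| 0.3 | √(1.4/20) = 0.265 | 0.55 |
| 0.5 | √(1.0/20) = 0.224 | 0.47 |
| 0.7 | √(0.6/20) = 0.173 | 0.36 |
| 0.8 | √(0.4/20) = 0.141 | 0.30 |

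**4. What would own baseline do in a two-arm comparison?** This was simulated with 300 trials per setting, 20 v 20, a six-level outcome and a two-sided 5% Wald test. The assumptions are an effect of 0.8 SD, a correlation of 0.4 between underlying frailty and own baseline, and frailty related to outcome only through own baseline.

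| r | Power, frailty only | Power, frailty + own baseline |
|---|---|---|
| 0.3 | 70% | 71% |
| 0.5 | 68% | 76% |
| 0.7 | 68% | 88% |
| 0.8 | 68% | 95% |

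The Monte Carlo standard error of one such figure is about √(0.68 × 0.32/300) = 2.7 percentage points, so the difference at 0.3 is not distinguishable from none.

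A second run of 200 trials per setting recorded the standard error of the log-odds ratio. Its median rose from 0.61 to 0.65 at r = 0.5 and from 0.61 to 0.69 at r = 0.7, while power rose from 68% to 78% and from 70% to 86%. Power rises because the adjusted log-odds ratio moves further from zero, not because its interval narrows.

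**The case against.** The best defence is that the plan is silent rather than wrong. For frailty, the baseline adjustment is the outcome's own baseline, so saying that SPPB and PROMIS also use the model could mean the same structure, with each outcome adjusted for its own starting value. That reading is possible, but the text names frailty status as the sole adjustment in the initial model. Nor does the reading rescue a one-arm model.

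One could also read exposure to the intervention as before versus after. Baseline would then be an outcome record rather than a covariate, and the model would need a term for repeated measures on the same person. The plan states neither.

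It is also fair to say that frailty is primary in section 3, that weight and glycaemic control are secondary, and that SPPB and PROMIS are not named there. That limits the weight of the point.

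A reader might infer more than the documents support:

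- *That baseline frailty is the only adjustment.* It is the only one in the initial model; a second set follows.
- *That omitting own baseline widens every interval.* That is linear-model reasoning. In a cumulative logit model the log-odds standard error did not shrink in simulation.
- *That treating the scores as ordinal throws information away.* If every value is kept as a level, it need not. The defect is that the levels are unstated, and with 20 people many could be sparse.
- *That the next study's sample size suffers.* Section 12.2 bases that on frailty, not on these scores.

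**Conclusion.** The point holds, as a minor one. The SPPB and PROMIS sentence in 12.3 and 12.4 points to a model whose stated covariates omit the scores' own baselines and whose levels are undefined. With Group B not enrolled, that model cannot yield an intervention effect for either measure. The second finding follows from the design and needs no assumed figure. That SPPB was measured at baseline is inferred from its place within the frailty assessment.

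The size of any benefit from own-baseline adjustment rests on assumed correlations and an assumed effect of 0.8 SD, and applies only if a two-arm comparison is made: roughly 8 to 20 percentage points of power at correlations of 0.5 to 0.7, and next to nothing at 0.3. For the enrolled arm, the case for paired change is that it can be estimated and uses the only comparator available, not that it is always more precise. It describes change over the study period. Without a control group, and with the pandemic falling within follow-up, it should not be reported as an effect of the intervention.

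**What to change.** In 12.3 and 12.4, replace the SPPB and PROMIS sentence with:

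> For SPPB total and each PROMIS score, the baseline to 6-month change is summarised as mean paired change, SD of change and 95% CI, with a rank-based check. Any regression or POCL model of these scores includes the same measure's baseline value as a covariate.

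If a POCL model is kept, list the levels used for each score. Because the April 2020 update in section 7 defers face-to-face frailty assessments for eight participants, report the actual interval for SPPB. Date the amendment, and say whether it was made before these outcomes were examined.

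The cost is small: one sentence in two places, using data already planned for collection. The paired mean treats the scores as interval-scaled, which the rank-based check partly answers, and a baseline term costs one parameter in a small model. Fasting glucose also lacks its own baseline and could be corrected in the same edit.
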